7.2.6 Enrollment

Once screening is completed, eligibility documents and checklist for all patients will be reviewed by and confirmed by investigator and/or Study Chair, CRC, and lead or senior CRC following UCSF HDFCCC SOP. Once eligibility is confirmed, approval to treat documentation indicating Cohort and dose level assignment as applicable will be provided to treating investigator and placed in study chart as confirmation of enrollment to proceed with protocol therapy.

7.2.6.1 Sub-site enrollment

The sub-site coordinator will send by secure e-mail or fax de-identified HIPAA-compliant copies of all consent and screening source documents to UCSF study team for eligibility confirmation. Once eligibility is confirmed by the Study Chair or designee, a document of approval to treat indicating Cohort and dose level assignment as applicable will be provided by secure e-mail by the UCSF CRC to the sub-site coordinator and treating investigator as confirmation of enrollment to proceed with protocol therapy.

7.3 Clinical procedures and assessments

7.3.1 Adverse event (AE) monitoring

The investigator or qualified designee will assess each subject to evaluate for potential new or worsening AEs as specified in the Schedule of Procedures (Section 7.1) and more frequently if clinically indicated. Adverse experiences will be graded and recorded throughout the study according to NCI CTCAE Version 4.03. Toxicities will be characterized in terms regarding seriousness, causality, toxicity grading, and action taken with regard to trial treatment. Please refer to Section 7.4 for further information on AE assessment and reporting.

7.3.2 Compliance with oral study drug

Patients will be provided a sorafenib drug diary to record time and dose of sorafenib administration each cycle (Appendix 14.7).

7.3.3 Vital signs

The investigator or qualified designee will obtain vital signs at the time points specified in the Schedule of Procedures (Section 7.1). Vital signs should include temperature, pulse, respiratory rate, oxygen saturation (pulse oximetry), weight and blood pressure. Height will be measured at screening only.

7.3.4 Complete physical examination

The investigator or qualified designee will perform a complete physical examination according to institutional practice for the management and monitoring of patients with liver cancers. Complete physical exams are required at screening, C1D1, C1D15, C2D1, C2D15, C3D1, and every D1 after Cycle 3. They are also required at Safety Follow-up 30 days and 100 days after lase dose (SFUV1 and SFVU2). Clinically significant abnormal findings during Screening should be recorded as medical history.

7.3.5 Eastern Cooperative Oncology Group (ECOG) performance scale

The investigator or qualified designee will assess ECOG status (see Appendix 14.2) at the time points specified in the Schedule of Procedures (Section 7.1).

7.3.6 Liver function assessment

The investigator or qualified designee will assess liver function by Child Pugh score (see Appendix 14.3) at the time points specified in the Schedule of Procedures (Section 7.1).

7.3.7 Tumor imaging and response assessment

Cross-sectional imaging with CT (preferred) or MRI abdomen plus pelvis and CT chest with/without or without contrast is required at screening then every 8 weeks (±14 days) until end of treatment. Multiphase/triphasic liver imaging should be included as appropriate. Additional baseline imaging such as PET scan, bone scan, or MRI brain are only required if clinically indicated by symptoms and/or to assess known bone metastases or other sites of known metastatic disease. All baseline evaluations will be performed as close as possible to the beginning of treatment and ≤ approximately 28 days before C1D1. The same imaging modality/modalities should be used if possible throughout study unless there is a clinical indication to use a different modality (i.e. based upon Radiology recommendation to better assess a target lesion, an event of new contrast allergy, etc.). RECIST 1.1 measurements will be performed by a radiologist or qualified investigator.

7.3.8 Laboratory procedures/assessments

The specific laboratory procedures/assessments to be performed in this trial are provided in Table 7.3.6-1 below, at time points listed in Schedule of Procedures (Section 7.1). Scheduled laboratory procedures and assessments should be performed at the study site of treatment.

Table 7.3.6-1 Laboratory procedures and assessments

Hematology	Chemistry	Urinalysis	Other
Hematocrit	Albumin	Blood	Serum β-human chorionic gonadotropin†
Hemoglobin	Alkaline phosphatase	Glucose	Urine β-human chorionic gonadotropin†
Platelet count	Alanine aminotransferase (ALT)	Protein	PT (INR)
WBC (total and differential)	Aspartate aminotransferase (AST)	Specific gravity	Thyroid stimulating hormone (TSH)
Red Blood Cell Count	Creatinine	Microscopic exam (If abnormal)	Total triiodothyronine (T3)
Absolute Neutrophil Count	Carbon dioxide (C02 or bicarbonate)	Urine pregnancy test †	Free thyroxine (T4)
	Calcium		AFP tumor marker
	Chloride		Hepatitis B or C viral load and serology (including Hepatitis D) as clinically indicated (see Tables 7.1-1 and 7.1-2 footnote 7)
	Glucose		
	Phosphorus		Blood samples for correlative studies*

Table 7.3.6-1 Laboratory procedures and assessments

Hematology	Chemistry	Urinalysis	Other
	Potassium		Archival tumor sample accessioning*
	Sodium		
	Magnesium		
	Total bilirubin		
	Direct bilirubin		
	Blood urea nitrogen (BUN)		

[†] Perform urine pregnancy test on WOCBP only. If urine pregnancy results cannot be confirmed as negative, a serum pregnancy test is required.

7.3.9 Tumor and blood sample collection and banking for correlative analyses

Archival tumor samples for all patients and peripheral blood samples for patients enrolled at UCSF will be obtained and stored for planned future exploratory and correlative analyses (see Sections 1.6 and 2.3) which will be performed in batch after completion of study and pending funding.

7.3.9.1 Archival tumor sample collection

In all patients, left-over diagnostic tumor block and/or slides from any tumor sampling procedure(s) (e.g. biopsy, fine needle aspiration, and/or resection specimens) performed prior to enrollment, during study treatment, and/or after treatment discontinuation due to progression will be obtained to determine tumor PD-L1 expression status, to characterize tumor immune infiltrates/T cell subsets, and (optional for UCSF patients only) to bank for future correlative analyses as part of the UCSF Hepatobiliary Tissue Bank and Registry (CC#124512) as a companion protocol to this study.

Formalin-fixed, paraffin-embedded (FFPE) tumor tissue blocks will be accessioned whenever available. In addition to blocks or if a block is not available, at least 10 unstained slides (prefer 10 μ m) plus 1 H&E slide from a tumor tissue block may be accessioned. Corresponding pathology reports from initial diagnosis and/or subsequent tumor sampling will be obtained. Specimens will be obtained from the Pathology Department for banking as soon as possible after consent and/or occurrence of post-enrollment tumor sampling and stored in the UCSF Biorepository. Correlative analyses using archival tissue samples will be performed in batch at completion of study and pending funding. See Appendix 14.8 for correlative specimen procurement and handling instructions.

7.3.9.2 Peripheral blood mononuclear cell (PBMC) collection

In all patients enrolled at UCSF, approximately 60 mL of whole blood will be collected into green top tubes (e.g. six 10 cc tubes filled approximately to 10 mL) at the time

^{*}See Section 7.3.7 and Appendix 14.8 for further information on research sample collection.

points listed in the Schedule of Procedures (Section 7.1). The tubes will be delivered directly to the UCSF Cancer Immunotherapy Lab for PBMC isolation then freezing for future analysis in batch at end of study and pending funding. See Appendix 14.8 for correlative specimen procurement and handling instructions.

7.3.9.3 Optional specimen banking

For patients enrolled at UCSF who consent to optional specimen banking as part of companion protocol CC#124512, all left-over blood and/or tumor samples will be banked under the UCSF Hepatobiliary Tissue Bank and Registry protocol. See Appendix 14.8 for correlative specimen procurement and handling instructions.

7.3.10 Electrocardiogram

A baseline electrocardiogram (ECG) should be obtained during screening at the study site per Section 7.1 in all patients.

7.4 Assessing and reporting adverse events (AE)

All subjects who receive at least one dose of study treatment will be evaluable for safety from the time of informed consent until 100 days after last dose of protocol therapy or the start of a new anti-cancer therapy after study discontinuation, whichever is earlier. Any serious adverse events (SAE) occurring later than 100 days after the last dose of protocol therapy or after start of new anti-cancer therapy also should be recorded and reported if assessed as at least possibly related to study drug or a protocol-specified procedure. All observations pertinent to the safety of the study treatment will be recorded and included in the final report.

Safety variables include the following: AEs, laboratory changes (complete blood counts, electrolytes, chemistry, and coagulation) if determined clinically significant by treating investigator and/or Study Chair, changes in vital signs (blood pressure, heart rate, respiratory rate, and temperature), and in some instances, changes in imaging findings if indicative of a safety event.

All AEs whether considered drug-related or not, will be recorded in case report forms in the OnCore® CTMS including Grade, attribution to one or both study drugs, other attribution(s), start/stop dates, and whether serious and/or unexpected. For all events, the relationship to treatment and the intensity of the event will be determined by the investigator. This trial will use the NCI CTCAE v.4.03 (https://ctep.cancer.gov/) for assessment of toxicity and SAE reporting with regard to toxicity grade. Investigators should refer to the Safety Information section of the current IB for sorafenib and nivolumab, including the DCSI (development core safety information), for the expected side effects of the study drugs.

7.4.1 AE and SAE definitions

7.4.1.1 Definition of adverse event (AE)

An Adverse Event (AE) is defined as any new untoward medical occurrence or worsening of a preexisting medical condition in a clinical investigation participant administered study drug and that does not necessarily have a causal relationship with this treatment. An AE can therefore be any unfavorable and unintended sign (such as an abnormal laboratory finding determined to be of clinical significance by the treating investigator or Study Chair), symptom, or disease temporally associated with the use of investigational product, whether or not considered related to the investigational product.

The causal relationship to study drug is determined by a physician and should be used to assess all adverse events (AE). The casual relationship can be one of the following:

- Related: There is a reasonable causal relationship between study drug administration and the AE.
- Not related: There is not a reasonable causal relationship between study drug administration and the AE.

Conditions that started before signing of informed consent and for which no symptoms or treatment are present until signing of informed consent are recorded as medical history (e.g. seasonal allergy without acute complaints). Conditions that started before signing of informed consent and for which symptoms or treatment are present after signing of informed consent, at unchanged intensity, are recorded as medical history (e.g. allergic rhinitis). Conditions that started or deteriorated after signing of informed consent will be documented as AEs.

7.4.1.2 Definition of serious adverse event (SAE)

An SAE is classified as any AE that, at any dose, meets any of the following criteria:

- 1. Results in death.
- 2. Is life-threatening.
 - a. The term 'life-threatening' in the definition refers to an event in which the patient was at risk of death at the time of the event, it does not refer to an event which hypothetically might have caused death if it were more severe.
- 3. Requires inpatient hospitalization or prolongation of existing hospitalization.
 - a. A hospitalization or prolongation of hospitalization will not be regarded as an SAE if at least one of the following exceptions is met:
 - b. The admission results in a hospital stay of less than 12 hours.
 - c. The admission is pre-planned. (i.e., elective or scheduled surgery

- arranged prior to the start of the study)
- d. The admission is not associated with an AE. (e.g., social hospitalization for purposes of respite care).
- e. However, it should be noted that invasive treatment during any hospitalization may fulfill the criterion of 'medically important' and as such may be reportable as an SAE dependent on clinical judgment. In addition, where local regulatory authorities specifically require a more stringent definition, the local regulation takes precedence.
- 4. Results in persistent or significant disability or incapacity.
 - a. Disability means a substantial disruption of a person's ability to conduct normal life's functions.
- 5. Is a congenital anomaly or birth defect.
- 6. Grade 3 or 4 hypersensitivity or infusion reaction to nivolumab.
- 7. Is another medically important serious event as judged by the investigator (defined as a medical event(s) that may not be immediately life-threatening or result in death or hospitalization but, based upon appropriate medical and scientific judgment, may jeopardize the subject or may require intervention [eg, medical, surgical] to prevent one of the other serious outcomes listed in the definition above.) Examples of such events include, but are not limited to, intensive treatment in an emergency room or at home for allergic bronchospasm; blood dyscrasias or convulsions that do not result in hospitalization.)
- 8. Suspected transmission of an infectious agent (eg, pathogenic or nonpathogenic) via the study drug is an SAE.
- Although pregnancy, overdose, potential drug-induced liver injury (DILI), and cancer are not always serious by regulatory definition, these events must be handled as SAEs.
- 10. Any component of a study endpoint that is considered related to study therapy should be reported as an SAE (e.g., death is an endpoint, if death occurred due to anaphylaxis, anaphylaxis must be reported).

7.4.2 Reporting of SAE to Bayer

All SAEs occurring from date of informed consent until 100 days after last dose of protocol therapy regardless of attribution should be reported to Bayer within 24 business hours/1 business day using a MedWatch Form 3500A (which can be accessed at http://www.accessdata.fda.gov/scripts/medwatch/ and in Appendix 14.9), using one of the mechanisms below. Any serious adverse events (SAE) occurring later than 100

days after the last dose of protocol therapy also should be recorded and reported if assessed as at least possibly related to study drug or a protocol-specified procedure.

Bayer SAE Electronic Mailbox:

Bayer SAE Facsimile:

Bayer USPS Address:

Global Pharmacovigilance - USA

Bayer Corporation

Reports for all Bayer products can also be phoned in via the Clinical Communications Dept.:

Bayer SAE Phone: (Medical Communications)

7.4.3 Reporting of SAE to BMS for protocol versions 1.0-3.0

For patients enrolled to Part 1 and Part 2 under protocol versions 1.0-3.0, all SAEs occurring from date of informed consent until 100 days after last dose of protocol therapy regardless of attribution should be reported to BMS within 24 business hours/1 business day using a MedWatch Form 3500A (which can be accessed at http://www.accessdata.fda.gov/scripts/medwatch/ and in Appendix 14.9), using one of the mechanisms below. Any serious adverse events (SAE) occurring later than 100 days after the last dose of protocol therapy also should be recorded and reported if assessed as at least possibly related to study drug or a protocol-specified procedure.

BMS SAE Facsimile Number:

Starting with protocol version 4.0 for patients enrolled to Part 2, nivolumab will be sourced as a standard of care therapy for advanced HCC in setting of Child Pugh B liver dysfunction and will not be provided by BMS. SAE reporting to BMS is not required for patients receiving treatment under protocol version 4.0 or later versions.

7.4.3.1 **SAE Reconciliation Reports**

The Study Chair or designee at UCSF will reconcile the clinical database SAE cases at all study sites (case level only) transmitted to BMS Global Pharmacovigilance

using the reporting form in Appendix 14.10. Frequency of reconciliation should be every 3 months and prior to the database lock or final data summary, or until activation of protocol version 4.0. BMS GPV&E will email, upon request from the Investigator, the GPV&E reconciliation report. Requests for reconciliation should be sent to the data elements listed on the GPV&E reconciliation report will be used for case identification purposes. If the Investigator determines a case was not transmitted to BMS GPV&E, the case should be sent immediately to BMS.

7.4.4 SAE follow up reports

If an ongoing SAE changes in its intensity or relationship to study drug or if new information becomes available, a follow-up SAE report should be sent within 24 business hours/1 business day to both Bayer (for patients enrolled to both Part 1 and 2) and BMS (for patients enrolled prior to protocol version 4.0 and not required after activation of protocol version 4.0) using the same procedures used for transmitting the initial SAE report. All SAEs should be followed to resolution or stabilization.

7.4.5 IND safety reporting

UCSF will report to the FDA all IND reportable events occurring in patients enrolled on this study (at UCSF or sub-site) using FDA Medwatch Form 3500A (which can be accessed at http://www.accessdata.fda.gov/scripts/medwatch/ and in Appendix 14.9). Reportable events must meet the definition in Federal Regulations (21 CFR §312.32):

- 1. Suspected adverse reaction (defined as a reasonable possibility that the investigational agent caused the adverse event)
- 2. Unexpected (not listed in the investigator brochure or package insert(s), or is not listed at the specificity or severity that has been observed)
- 3. Serious (as defined in Section 7.4.1.2)

If the adverse event does not meet all three of the definitions, it should not be submitted as an expedited IND safety report. The timeline for submitting an IND safety report to FDA is no later than 15 calendar days after the Investigator determines that the suspected adverse reaction qualifies for reporting (21 CFR 312.32(c)(1)). Any unexpected fatal or life-threatening suspected adverse reaction will be reported to FDA no later than 7 calendar days after the Investigator's initial receipt of the information (21 CFR 312.32(c)(2)).

Any relevant additional information that pertains to a previously submitted IND safety report will be submitted to FDA as a Follow-up IND Safety Report without delay, as soon as the information is available (21 CFR 312.32(d)(2)).

A copy of all 15 Day Reports and Annual Progress Reports will be submitted as required by FDA.

The Study Chair or designee will cross reference this submission according to local regulations to the Bayer and/or BMS Investigational Compound Number (IND) at the time of submission, based upon investigator attribution of causality. Additionally, Study Chair or designee will submit a copy of these reports to Bayer and BMS at the time of submission to FDA.

7.4.6 Expected adverse events

For this study, the applicable reference document is the most current version of the investigator's brochure (IB) for each drug. Overview listings of frequent events that have occurred so far in the clinical development are shown in the current IBs. If relevant new

safety information is identified, the information will be integrated into an update of the corresponding IB and distributed to any participating site(s).

The expectedness of AEs and SAEs will be determined locally by the treating investigator and Study Chair or designee. For reportable SAE, expectedness will also be assessed by Bayer and BMS according to the applicable reference document and according to all local regulations.

7.4.7 Pregnancies

The investigator must report to Bayer and BMS any pregnancy occurring in a study subject, or in his partner, during the subject's participation in this study. The report should be submitted within the same timelines as an SAE, although a pregnancy per se is not considered an SAE.

For a study subject, the outcome of the pregnancy should be followed up carefully, and any abnormal outcome of the mother or the child should be reported.

For the pregnancy of a study subject's partner, all efforts should be made to obtain similar information on course and outcome, subject to the partner's consent.

For any reports of pregnancy occurring in study subject or WOCBP partner, a Medwatch form (Appendix 14.9) should be used for reporting as an SAE.

8. Statistical methods and determination of sample size

8.1 Analysis sets

8.1.1 DLT population (Part 1)

Subjects must receive 2 doses of nivolumab and at least 75% of sorafenib doses within 28 days (1 cycle), or experience a qualifying DLT event (Section 6.2.3), to be evaluable for DLT. Patients enrolled to Part 1 who are determined ineligible after enrollment and/or who are not evaluable for the endpoint of DLT will be replaced (see Section 5.2.2).

8.1.2 Safety population (Parts 1 and 2)

The safety population will include all enrolled patients who receive at least one dose each of sorafenib and nivolumab and have the potential to complete 1 cycle (28 days) of safety assessments. All patients will be evaluable for toxicity and safety assessment from the time of their first treatment with the investigational combination. Patients who are determined ineligible after enrollment or who are not evaluable for safety (e.g. due to withdrawal of consent or discontinuation due to complications of HCC or underlying liver disease assessed as not related to tumor progression and not treatment-related

toxicity before completing 1 cycle) will not be included in safety analyses (see Section 5.2.2).

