5.3.2 Replacement

Patients enrolled to Part 1 or Part 2 who are determined ineligible after enrollment and/or who are not evaluable for the endpoints of DLT or safety will be replaced. See "Statistical methods and determination of sample size" in Section 8.0.

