8.2 Statistical and analytical plans

8.2.1 Primary endpoints

Primary and secondary endpoints will be measured in evaluable patients as defined in Section 8.1.

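### The denominator for the Part 2 primary safety rate drops some dosed patients, with nothing to keep those who already had a related grade ≥3 event, and it differs from Section 7.4

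*Combined protocol and SAP*

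**What the plan says.** Section 8.2.1 fixes the analysis sets: "Primary and secondary endpoints will be measured in evaluable patients as defined in Section 8.1". Section 8.2.1.2 names no set of its own for the Part 2 rate, so the reader is sent to 8.1.2.

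Section 8.1.2 has three parts:

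- **Inclusion.** The set is to "include all enrolled patients who receive at least one dose each of sorafenib and nivolumab and have the potential to complete 1 cycle" of safety assessments.
- **Start of evaluability.** "All patients will be evaluable for toxicity and safety assessment from the time of their first treatment with the investigational combination".
- **Exclusion.** The excluded group is "Patients who are determined ineligible after enrollment or who are not evaluable for safety". The examples given are consent withdrawal, and stopping in cycle 1 for complications of the cancer or the underlying liver disease that are judged to be neither progression nor treatment toxicity. These patients are left out of safety analyses.

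Section 5.3.2 adds that patients found ineligible, or those "who are not evaluable for the endpoints of DLT or safety will be replaced".

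Section 7.4 differs: "All subjects who receive at least one dose of study treatment will be evaluable for safety". It requires one dose of study treatment, not one of each drug, and makes no exclusion for late ineligibility or early stopping. It also says: "All AEs whether considered drug-related or not, will be recorded in case report forms".

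**The concern.** A safety rate should count everyone exposed. Under 8.1.2, a dosed patient can leave both numerator and denominator because of something learned or judged after dosing, even if a related grade ≥3 event has already occurred. The reference to treatment-related toxicity in the exclusion sentence concerns why a patient stopped. It does not protect a patient who had one related grade ≥3 event and then stopped for a different, unrelated liver complication, or who was later found ineligible.

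The phrase about not being evaluable for safety is defined only by examples, so two analysts could build different denominators from the same data. Section 7.4 gives a third version.

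The rate feeds a stated decision. Section 8.2.1.2 calls a rate of at most 50% acceptable, and Section 8.2.2.3 makes acceptable Part 2 safety a condition for considering a larger study.

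**Working it through.** **Inputs.** From 8.2.1.2: n = 12; benchmark ≤50%; planned 95% intervals of (0.07, 0.60), (0.14, 0.70), (0.22, 0.78) and (0.30, 0.86) at rates of 30%, 40%, 50% and 60%; cited single-agent rates of 24.5%, 28% and 30–36%. The number of excluded patients is an assumption, because the documents give none.

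**The plan's own figures.** The Wald interval p ± 1.96√(p(1−p)/n) at the nearest whole count reproduces all four:

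- 4/12: (0.067, 0.600)
- 5/12: (0.138, 0.696)
- 6/12: (0.217, 0.783)
- 7/12: (0.304, 0.862)

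They assume 12 evaluable patients and take no account of the exclusion rule.

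**One excluded patient.**

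- The patient had an event and was replaced: 7/13 = 53.8% among all treated (exact 95% CI 0.25 to 0.81) becomes 6/12 = 50.0% (0.21 to 0.79).
- The patient had no event and was not replaced: 6/12 = 50.0% becomes 6/11 = 54.5% (0.23 to 0.83).

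So the rate can move either way across the benchmark.

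**Two of 14 treated excluded, 12 kept.** Let X ~ Bin(12, p) be the events in the 8.1.2 set and Y the events among the two excluded. The two sets disagree about ≤50% in two cases only:

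- X = 6, Y = 2: 6/12 = 50.0% against 8/14 = 57.1%
- X = 7, Y = 0: 7/12 = 58.3% against 7/14 = 50.0%

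If exclusion is unrelated to events, Y ~ Bin(2, p), and P(disagree) = P(X=6)·p² + P(X=7)·(1−p)². If neither excluded patient had an event it is P(X=7). If both did it is P(X=6).

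| True rate p | Unrelated to events | Neither had an event | Both had an event |
|---|---|---|---|
| 24.5% | 0.002 + 0.006 = 0.008 | 0.010 | 0.037 |
| 30% | 0.007 + 0.014 = 0.021 | 0.029 | 0.079 |
| 36% | 0.018 + 0.027 = 0.045 | 0.067 | 0.138 |
| 50% | 0.056 + 0.048 = 0.105 | 0.193 | 0.226 |

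**One of 12 excluded, no replacement.** With X ~ Bin(11, p), the sets disagree only when X = 6 and the excluded patient had no event (6/11 against 6/12). P = P(X=6)·(1−p), which is 0.040 at 30%, 0.069 at 36% and 0.113 at 50%.

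The figures that assume exclusion is unrelated to events show how often the choice of set would change the reading against 50%. They do not show bias. Bias arises only if exclusion is related to having an event, which the last two table columns illustrate at their extremes.

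**The case against.** The strongest case is that the harmful route is narrow and the consequence modest.

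- Patients who stop in cycle 1 because of treatment-related toxicity are not named as excluded.
- Consent withdrawal is an example, not an automatic exclusion, and the one-cycle limit can be read as applying to it too.
- Both drugs start on C1D1 (Sections 6.3 and 6.3.1), so few patients should receive only one.
- Eligibility is confirmed before treatment (Sections 7.2.6 and 7.2.6.1), so late ineligibility should be uncommon.
- The sentence on when evaluability starts could support keeping anyone with an observed event.
- Section 7.4 concerns adverse-event reporting, and it requires all pertinent safety observations to go into the final report, so an excluded patient's event should still be visible.
- The Abstract closes accrual at 12 enrolled or on 30 April 2022, whichever comes first. That makes the 13- and 14-patient illustrations less likely than a case with 12 or fewer.
- Requiring both drugs and confirmed eligibility fits an objective about the combination in Child Pugh B patients.

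Most of this stands, and it limits the size. It does not settle which patients form the primary denominator. The explicit exclusion follows the sentence on evaluability, which can be read as fixing only the starting time; I do not claim that 8.1.2 contradicts itself. Reporting an event elsewhere does not restore it to the primary proportion. The DLT and response sets in 8.1.1 and 8.1.3 carry event wording for patients otherwise not evaluable, though not clearly for late ineligibility; 8.1.2 has none.

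**Conclusion.** The concern holds and should be fixed. Followed as written, 8.1.2 can remove dosed patients from both numerator and denominator of the primary safety rate on post-dosing grounds, and it differs from 7.4 on who is evaluable.

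The size is unknown. With one or two exclusions out of 12 to 14 treated, single-patient shifts are about 4 to 5 percentage points. If exclusion is unrelated to events, the two sets fall on opposite sides of 50% with a probability of roughly 1% to 11% over true rates of 24.5% to 50%. In the two-exclusion case this rises to as much as 23% if the excluded patients all had events or all had none. The cited 24.5–36% rates are for single agents, and the combination may run higher.

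The direction depends on who is left out. Every shift is small beside the planned interval, and 50% is a benchmark in a descriptive pilot, not a test. At risk are the primary proportion and the safety tables, not the underlying data.

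**What to change.** - **Section 8.1.2:** define the safety population as all patients who receive at least one dose of sorafenib or nivolumab, in line with 7.4. Use it for the Part 2 primary endpoint and all safety tables.
- **Section 5.3.2:** state that replaced patients remain in the safety analysis.
- **Sections 8.1.1 to 8.1.3:** correct the pointer to Section 5.2.2, which does not exist; replacement is in 5.3.2.
- **Sensitivity analysis:** keep a labelled analysis in eligible Child Pugh B patients who received both drugs. List each treated patient it leaves out, the reason, and whether a related grade ≥3 event occurred.

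A clause that only rescues patients with events would not do, because it keeps events and drops non-events. If one patient with an event and one without meet the exclusion wording, an all-treated 6/12 = 50.0% becomes 6/11 = 54.5%.

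The cost is wording; no new data are needed. The denominator may exceed 12. It may also include a patient who received one drug only, or one later found not to be Child Pugh B, which fits the stated objective less closely. The sensitivity analysis covers both. The change should be made before the Part 2 rate is analysed.
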